## **3 STUDY IMPLEMENTATION**

### **3.1 STUDY DESIGN**

This is a multi-center, randomized, open-label, controlled trial to evaluate the efficacy and tolerability of Hydroxychloroquine Sulfate (HCQ) in adult Patients with mild to moderate coronavirus disease (COVID-19) compared to standard of care treatment (SOC). The primary endpoint for the study is to evaluate the efficacy of HCQ, with respect to the time to negatively rRT-PCR assessments from the randomization date up to 14 days. The secondary endpoint is to evaluate the efficacy of HCQ in the aspect of virological assessments and the change of clinical symptoms. In addition, the safety and tolerability of HCQ will be evaluated during treatment period in COVID-19 patients.

The study will employ an open-label parallel design, to evaluate the efficacy and safety between hydroxychloroquine sulfate (plaquenil) and controlled standard of care treatment. The administration plan of HCQ is 400 mg bid on Day 1 and 200 mg bid for 6 days on Day 2-7. All of the enrolled subjects will receive standard of care. The comparison group will receive standard of care, i.e., supportive treatment for subjects with mild COVID-19 clinical illness, and antimicrobial therapy for subjects who developed moderate COVID-19 clinical illness (ceftriaxone 2gm daily for 7 days ± azithromycin 500mg on Day1 and 250mg on Day2-5; or levofloxacin 750 mg daily for 5 days, or levofloxacin 500mg daily or moxifloxacin 400mg daily for 7-14 days for the subjects who had allergic history to ceftriaxone or azithromycin, or per physician's discernation). Oseltamivir 75 mg bid for 5 days will be given for subjects who have concomitant influenza A or B infection. The subjects will be randomly assigned to a 2:1 ratio to receive HCQ + SOC, or SOC alone. The estimated case number will be 30:15. No dose reduction, modification, or change in the frequency of HCQ will be recommended during the study period.

The investigators may determine to switch to HCQ treatment arm on Day 8 if the subjects developed progression of pneumonia clinically, or roentegenographically, or had persistent high viral load without 10 log of decline, compared to baseline data.

An independent data monitoring committee (IDMC) will be instituted to ensure external objective

medical and/or statistical review of efficacy to protect the ethical interests and well-being of participants and to protect the scientific validity of the study.

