### **3.5 CRITERIA FOR REMOVAL FROM PROTOCOL THERAPY AND OFF STUDY CRITERIA**

#### **3.5.1 Off-Study Criteria**

Participants who developed adverse events including grade 3/4 liver toxicity, grade 3 allergic reaction, or other severe adverse events (including progression to the stage of severe pneumonia)

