### **4 CONCOMITANT MEDICATIONS/MEASURES**

Concomitant medications will be recorded well.

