### **6 DATA COLLECTION AND EVALUATION**

#### **6.1 DATA COLLECTION**

The study will use eCRF/EDC for data collection. Safety laboratory data will be entered into eCRF by authorized personnel at Investigational sites. Real-time RT-PCR data will be managed and stored within the laboratory information management system and only the date and time of specimens are recorded in the eCRF. Safety laboratory data will be integrated with the consolidated clinical data before database lock.

All records should be kept in conformance to applicable national laws and regulations.

Adverse events will be recorded according to the Division of AIDS (DAIDS) Table for Grading the Severity of Adult and Pediatric Adverse Events(Appendix 3), and will be coded using the current MedDRA thesaurus (Version 19.0); concomitant medication will be coded using World Health Organization Collaborating Centre for Drug Statistics Methodology Anatomical Therapeutic Chemical/defined daily dose (WHOC ATC/DDD).

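### Controls may be switched to HCQ on Day 8, inside the Day 14 primary window; if HCQ works when started then, the as-randomised Day 14 result understates HCQ + SOC versus SOC alone

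*Protocol*

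**What the plan says.** Protocol section 3.1 (Study Design) states that subjects are "randomly assigned to a 2:1 ratio to receive HCQ + SOC, or SOC alone", with 30 and 15 planned, and gives the primary endpoint as "time to negatively rRT-PCR assessments from the randomization date up to 14 days". The HCQ course in the randomised arm is "400 mg bid on Day 1 and 200 mg bid for 6 days on Day 2-7".

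The same section says that investigators may decide to "switch to HCQ treatment arm on Day 8 if the subjects developed progression of pneumonia clinically, or roentegenographically, or had persistent high viral load". The viral-load trigger reads in full "had persistent high viral load without 10 log of decline, compared to baseline data". Control subjects are not named, but only they can move into the HCQ arm.

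Section 6.2.1 schedules the primary rRT-PCR on Day 0 and every second day to Day 14. Section 6.3.1 has a viral-load AUC over the same days and a virological clearance rate at Day 8, both secondary. Section 3.5.1 lists as an off-study reason a severe adverse event, "including progression to the stage of severe pneumonia". On data capture, section 4 says "Concomitant medications will be recorded well". For rRT-PCR, section 6.1 says that "only the date and time of specimens are recorded in the eCRF".

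**The concern.** Three of the seven post-baseline assessments (Days 10, 12 and 14) come after the permitted switch. From Day 8 a switched control is no longer on SOC alone, so the later part of the primary comparison is not wholly the contrast that section 3.1 describes.

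The switch is made by investigators who know the allocation, and one trigger, persistent high viral load, is closely tied to the primary outcome. The controls who can still convert after Day 8 are therefore the ones exposed to switching. With only 15 controls, a few switches matter.

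If late-started HCQ speeds clearance, the arms are drawn together after Day 8. The estimate shrinks, power is lost, and a small Day 14 difference is harder to interpret: it may reflect a weak drug, HCQ use among controls, or both.

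**Working it through.** **What can be reproduced.** 30:15 agrees with 2:1. It cannot be reproduced as a sample size, because the protocol gives no effect size, power, clearance rate or switch rate. Everything below rests on assumed values and shows direction and range only.

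**Assumptions.** 30 HCQ and 15 control subjects; visits every 2 days to Day 14; exponential clearance with control median 10 days (rate λ = ln 2 / 10); HR for becoming negative 2.5; two-sided 5% log-rank test. A share *s* of controls still positive at Day 8 switches and takes the HCQ rate from Day 8 plus a lag *L*.

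**Step 1: controls exposed.** Still positive at Day 8: exp(−8λ) = 2^(−0.8) = 0.574, and 15 × 0.574 = 8.6 subjects. Switching 25, 50 or 100% of them is about 2, 4 or 9 subjects.

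**Step 2: Day 14 negativity.**
- HCQ arm: 1 − 2^(−14 × 2.5/10) = 1 − 2^(−3.5) = 91.2%.
- Controls, no switching: 1 − 2^(−1.4) = 62.1%; difference 29.1 points.
- All switched, no lag: 1 − 2^(−0.8 − 1.5) = 79.7%; difference 11.5 points.
- All switched, two-day lag: 1 − 2^(−1.0 − 1.0) = 75.0%; difference 16.2 points.
- All switched, four-day lag: 1 − 2^(−1.2 − 0.5) = 69.2%; difference 21.9 points.

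**Step 3: power and HR estimate.** Simulation, 20,000 runs per scenario, standard error at most 0.0036. A fresh run agreed to within 0.01.

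| Lag in switched controls | 0% | 25% | 50% | 75% | 100% | HR estimate, 0% to 100% |
|---|---|---|---|---|---|---|
| None | 0.70 | 0.64 | 0.58 | 0.51 | 0.44 | 2.58 to 2.00 |
| 2 days | 0.70 | 0.67 | 0.63 | 0.59 | 0.55 | 2.58 to 2.21 |
| 4 days | 0.70 | 0.68 | 0.67 | 0.66 | 0.63 | 2.58 to 2.41 |

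For other effects with no lag, at 0/50/100% switched: HR 1.5 gives 0.18/0.13/0.10, HR 2 gives 0.45/0.35/0.25, and HR 3 gives 0.86/0.76/0.63. With HR 1, rejection stays at 4.9 to 5.5%.

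**Step 4: both arms censored at Day 8.** Power is 0.57 at HR 2.5. It exceeds the Day 14 analysis only above a switch share of about 55% (no lag) or 88% (two days), and never with four days. If the lag also applies in the HCQ arm, the Day 8 cut has no advantage: 0.35 against 0.53 falling to 0.36 with two days, and 0.18 against 0.36 falling to 0.30 with four days. If instead the HCQ effect ends with the course on Day 7, the Day 8 cut (0.51) exceeds Day 14 at every share (0.43 falling to 0.18 with no lag).

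**Step 5: existing Day 8 clearance rate.** Expected 1 − 2^(−2) = 75.0% against 1 − 0.574 = 42.6%; power of Fisher's exact test at 30 v 15 is 0.51.

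**Step 6: viral-load AUC.** Assume linear log10 decline with slope difference *d* per day and no detection floor. The Day 0-14 difference is 14²*d*/2 = 98*d*. A switch at Day 8 removes (6 − *L*)²*d*/2, that is 18*d*, 8*d* or 2*d* at lags of 0, 2 or 4 days. If all 15 controls switched, the loss would be 18, 8 or 2%. If only the still-positive 57.4% switch, it is 0.574 times these: about 10.5, 4.7 or 1.2%.

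**Step 7: censoring switchers alone.** With gamma frailty (variance 0.5), true HR 1, and the slowest half of still-positive controls censored at Day 8, the HR estimate is 0.88. It is 0.98 with both arms cut at Day 8, and 0.98 with no switching.

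**The case against.** The strongest reply is that this is a deliberate design choice. The allocation sentence describes what subjects are assigned to, the switch is stated openly in the same section, and later access for progressing controls is a common ethical choice. Read so, the trial compares HCQ from Day 1 with SOC plus optional HCQ from Day 8, and the handling of switches may sit in a SAP that is not shown. Much of this stands: the as-randomised result validly estimates that comparison, and the absence of an analysis rule is not the finding. The finding is the design feature. No SAP can recover SOC-alone data after Day 8 or fix the order of the Day 8 specimen and the first switched dose.

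It is also fair that the existing Day 8 clearance rate helps (0.51 against 0.57 for a Day 8 time-to-event analysis), that losses are modest with few switches or a slow effect, and that power is low for smaller effects anyway (0.18 at HR 1.5 with no switching).

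Stronger readings that a reader might infer, and why they fail:
- *Nearly every control will switch, because the 10 log wording excludes almost nobody.* The switch is discretionary and the trigger also requires a viral load that is persistent and high. The protocol gives no rate, so full switching is only an outer bound.
- *The test is invalid.* Under no effect, switching changes nothing, and rejection stays near 5%.
- *A null Day 14 result could not be interpreted.* The Day 0-8 part of the curves and the Day 8 clearance rate are free of switching, apart from same-day timing.
- *Discharge and mortality are biased too.* Section 3.5.1 may take subjects who progress to severe pneumonia off study rather than onto HCQ. No claim is made there.

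**Conclusion.** The point holds in conditional form and should be fixed. If HCQ works when started on Day 8, the as-randomised Day 14 comparison understates HCQ + SOC versus SOC alone. Conversions by Day 8 are unaffected, provided the Day 8 specimen precedes the switch, which the protocol does not state.

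Under the assumed base case the loss of power runs from 0.02 (25% switched, four-day lag) to 0.26 (all still-positive controls switched, no lag). The AUC is less exposed, at about 1 to 10% of its difference with all still-positive controls switched. The true size cannot be derived from the protocol. Confidence is medium, because switch rate, effect, lag and clearance rate are all assumed.

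**What to change.** Reconcile the Day 8 switch in section 3.1 with the Day 14 windows in section 6.2.1 and, for the viral-load AUC, section 6.3.1. The clinical switch rule and the meaning of the 10 log text are for the sponsor to settle.

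1. State that the scheduled Day 8 specimen is collected before any switched dose, and record the date and time of that dose. Only then is a Day 8 analysis free of switching.
2. Keep the Day 14 comparison by randomised arm and label it the treatment-policy result.
3. Pre-specify beside it a time-to-negative comparison with all subjects in both arms censored at the Day 8 specimen, and an AUC over Days 0-8. Read both with the existing Day 8 clearance rate.
4. Report the number and timing of switches. Do not censor switchers alone, because switching depends on the outcome.

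The cost is wording in three sections and one added data item. No extra specimens or subjects are needed, since specimen times are already captured and concomitant medications recorded. The downside is that the Day 8 comparison has less power than Day 14 when few controls switch (0.57 against 0.70 at none, 0.64 at 25% with no lag) or when the effect is delayed in both arms (0.35 against 0.53 with two days and no switching). It therefore accompanies the Day 14 result and does not replace it.

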### **6.3 SECONDARY ENDPOINTS**

#### **6.3.1 Evaluation of Efficacy**

- Virological clearance rate at day 8
- AUC of viral load on day 0, 2, 4, 6, 8, 10, 12, 14

For the above 2 secondary efficacy evaluations, the type of respiratory tract specimens in each assessment day should be the same with Day 0.

- Time to Clinical recovery (TTCR):

TTCR is defined as the time (in hours) from randomization (active or placebo) until normalization of fever, respiratory rate, and oxygen saturation, and alleviation of cough, sustained for at least 72 hours.

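### The Day 8 switch rule in Section 3.1 turns on a 10 log fall in viral load; on the log10 scale no subject still called high could plausibly show one, so the condition excludes nobody.

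*Protocol*

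**What the plan says.** Section 3.1 of the protocol contains a crossover rule: "The investigators may determine to switch to HCQ treatment arm on Day 8". There are two kinds of trigger. The first is worsening pneumonia: "if the subjects developed progression of pneumonia clinically, or roentegenographically". The second is virological: "or had persistent high viral load without 10 log of decline, compared to baseline data".

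The same section describes an open-label, 2:1 design and gives its planned size: "The estimated case number will be 30:15". Section 2.4 makes Day 0 the baseline.

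Outside this rule, viral load appears as a quantity in Section 6.3.1, as a secondary endpoint: "AUC of viral load on day 0, 2, 4, 6, 8, 10, 12, 14". That section also ties the specimen type to Day 0: "For the above 2 secondary efficacy evaluations, the type of respiratory tract specimens in each assessment day should be the same with Day 0". The protocol states no log base, unit, detection limit or cut-off for a high load, and nothing elsewhere corrects or explains the figure of 10 log.

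**The concern.** The virological trigger reads as two conditions joined together: the load is still high, and it has not fallen by a stated amount. The second condition is useful only if someone who meets the first could fail it. It should hold back subjects who are still high but are falling at an acceptable rate on standard of care (SOC). A 10^10-fold fall looks far too large for that purpose.

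This figure is a treatment-decision threshold that site investigators apply during an open-label, multi-center trial. It therefore has to work in the protocol itself, because an analysis plan cannot undo a switch already made. It is also the only number attached to the viral-load route. If it excludes nobody, any SOC subject whose load is called high on Day 8 may be given HCQ, however well the load is falling. The primary endpoint is still being observed at that point, since it is defined as the "time to negatively rRT-PCR assessments from the randomization date up to 14 days".

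**Working it through.** The protocol gives no derivation for 10 log, so there is no calculation of its own to reproduce. The check asks when the decline condition could exclude someone.

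**Inputs**

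- Required decline: t = 10 (Section 3.1).
- Scale: log10. This is an assumption, as the usual scale for viral load; the protocol names none.
- Cut-off for *high*, H: 10^3 to 10^6 copies/mL (assumed).
- Baseline load, B: 10^4 to 10^11 copies/mL (assumed).
- Day 8 load: L8.

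**Step 1. The rule as a formula.** A subject qualifies by this route if

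L8 ≥ H and log10(B) − log10(L8) < t.

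The second condition excludes a subject who meets the first only if the fall is at least t while L8 ≥ H. That requires

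log10(B) ≥ log10(H) + t.

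**Step 2. Baseline needed with t = 10.**

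| Assumed H (copies/mL) | log10(H) + 10 | Baseline needed |
|---|---|---|
| 10^3 | 3 + 10 = 13 | 10^13 |
| 10^4 | 4 + 10 = 14 | 10^14 |
| 10^5 | 5 + 10 = 15 | 10^15 |
| 10^6 | 6 + 10 = 16 | 10^16 |

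The smallest of these exceeds the largest assumed baseline by 13 − 11 = 2 log10, a factor of 100.

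**Step 3. Load left after a 10 log10 fall, L8 = B / 10^10.**

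- B = 10^8: 0.01 copies/mL
- B = 10^10: 1 copy/mL
- B = 10^11: 10 copies/mL
- B = 10^13: 1,000 copies/mL

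Over the assumed baselines, no result reaches even the lowest cut-off of 10^3.

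**Step 4. Largest fall that leaves a load still high, log10(B) − log10(H).**

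- B = 10^8: 8 − 6 = 2 to 8 − 3 = 5 log10
- B = 10^10: 10 − 6 = 4 to 10 − 3 = 7 log10
- B = 10^11: 11 − 6 = 5 to 11 − 3 = 8 log10

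All are below 10, so the decline condition is met automatically.

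**Step 5. The same check with t = 1.** The baseline needed becomes 10^(3+1) = 10^4 to 10^(6+1) = 10^7 copies/mL, which lies inside the assumed range. A 1 log10 threshold could therefore exclude someone.

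**Example.** A load falls from 10^8 to 10^6, which is 8 − 6 = 2 log10, and is still called high. As written, 2 < 10, so the subject may switch. With a 1 log10 threshold, 2 ≥ 1, so the subject may not.

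**The case against.** The strongest case on the other side is that little follows from the error. The switch is permitted, never required. The pneumonia triggers work as written. The only subjects affected are SOC subjects without progression whose load is still called high although it has fallen by at least the amount intended, and the protocol has no data from which to count them. All of this stands. It limits the size of the point but does not make the threshold usable.

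The figure may also be a slip for 1.0 log or for log10, or a decimal point may have been lost when the PDF was read. The text cannot settle this. Decimals and superscripts survive elsewhere (the eGFR criterion in Section 2.1.2), so lost text is only a possibility. If the source file shows a different figure, this point should be rechecked against it.

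A reader might go further in several directions that the document does not support:

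- *Another log base.* Ten natural logs is 22,026-fold (4.34 log10) and ten base-2 logs is 1,024-fold (3.01 log10). Either could exclude someone, from baselines of about 10^7.34 and 10^6.01 upward if H = 10^3. Nothing in the text points to these bases, so the point rests on log10 alone.
- *Subjects who have turned negative could be switched.* The trigger requires a load that is still high. The decline phrase could instead be meant to explain that wording. Even so, 10 log10 would not be a workable test: with an assumed detection limit of 10^2, the largest measurable fall from 10^11 is 11 − 2 = 9 log10.
- *Power is lost or the primary endpoint is biased by this figure.* Exposure of the Day 10 to 14 assessments to crossover comes from allowing a switch at all, and would remain after correction.
- *At most 15 subjects are involved.* Section 2.3 provides for replacement subjects, so the SOC arm could exceed 15.
- *The missing cut-off for a high load is itself an error.* It is missing detail, not a wrong statement.

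**Conclusion.** The point holds in a limited form and should be corrected. On the log10 scale, the only numeric limit on the viral-load route to crossover excludes nobody, so the route is governed by the unquantified idea of a persistently high load. The threshold is wrong by a wide margin: at least 2 log10 separate the highest assumed baseline from the lowest baseline at which the condition could matter, and 16 − 11 = 5 log10 at the highest assumed cut-off.

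The conclusion rests on three things: the log10 scale, the assumed loads and cut-offs, and reading the trigger as two joint conditions. It does not depend on a fine choice within the assumed ranges. What the error would do in practice is unknown, because the protocol gives no viral-load data and leaves the switch to judgment.

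**What to change.** In Section 3.1, replace 10 log with an attainable decline and name the scale. The intended value is probably 1 log10, a 10-fold fall, but the sponsor should confirm it. State that the decline is measured from Day 0 to Day 8 on the same specimen type. A numeric cut-off for a high load would help sites apply the rule consistently, but it is an optional addition.

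The cost is one wording change. Section 6.3.1 already plans viral load on Days 0 and 8 with matched specimens, so no extra sampling is needed. There are two small consequences. Fewer SOC subjects without progression may be eligible to switch. The laboratory must also report both loads to investigators in time for the Day 8 decision. Section 6.1 keeps PCR results in the laboratory system and puts only specimen date and time in the eCRF, so the sponsor should check that this reporting happens.

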### **3.5 CRITERIA FOR REMOVAL FROM PROTOCOL THERAPY AND OFF STUDY CRITERIA**

#### **3.5.1 Off-Study Criteria**

Participants who developed adverse events including grade 3/4 liver toxicity, grade 3 allergic reaction, or other severe adverse events (including progression to the stage of severe pneumonia)

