## **2 ELIGIBILITY ASSESSMENT AND ENROLLMENT**

### **2.1 ELIGIBILITY CRITERIA**

#### **2.1.1 Inclusion Criteria**

1. Male and female age between 20-79 years
2. Patients who had fever (central temperature  $\geq 38^{\circ}\text{C}$ ) or acute upper respiratory symptoms and laboratory confirmation (rRT-PCR) for COVID-19, with available same type of upper respiratory tract specimens from screening evaluation to the initial testing within 4 days of initial testing
3. Patients have mild (no pneumonia) to moderate disease (pneumonia without respiratory distress) according to the following World Health Organization (WHO) definition of COVID-19 clinical syndromes:

- Mild (Mild illness):

Patients with uncomplicated upper respiratory tract viral infection, may have non-specific symptoms such as fever, fatigue, cough (with or without sputum production), anorexia, malaise, muscle pain, sore throat, dyspnea, nasal congestion, or headache. Rarely, patients may also present with diarrhoea, nausea and vomiting.

- Moderate (Pneumonia):

Adult with pneumonia but no signs of severe pneumonia and no need for supplemental oxygen.

4. Willing and able to comply with the study procedure and sign a written informed consent

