## **2.3 RANDOMIZATION (OR STRATIFICATION) PROCEDURES (APPLICABLE FOR RANDOMIZED CONTROLLED TRIALS)**

After signing the written informed consent form, 3-digits screening number contains the first letter of S (starting from S01) will be assigned to subject sequentially. Subject screened but not eligible will have the screening number only.

Subjects who meet all study criteria after the screening evaluation will be randomly assigned to in a 2:1 ratio, stratified with mild illness (no pneumonia) and moderate disease (with pneumonia), to receive hydroxychloroquine or have standard of care (SOC) treatment. A randomization number (starting from 001) will be sequentially assigned to an eligible subject. Replacement subjects will be assigned the corresponding number, starting from 101 (i.e., the replacement subject for 005 will be assigned a number of 105, etc.).

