#### **6.2 CRITERIA OF PRIMARY ENDPOINTS**

##### **6.2.1 Primary efficacy endpoints**

- Transition time of SARS-CoV-2 nucleic acid rRT-PCR from positive results to negative results in respiratory tract specimen on day 0, 2, 4, 6, 8, 10, 12, 14. For evaluation of primary efficacy endpoint, the type of respiratory tract specimens in each assessment day should be the same with Day 0.

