#### Normalization and alleviation criteria:

- Fever -  $\leq 36.9^{\circ}\text{C}$  or -axilla,  $\leq 37.2^{\circ}\text{C}$  oral,
- Respiratory rate -  $\leq 20/\text{minute}$  on room air,
- Oxygen saturation -  $\geq 94\%$  on room air,
- Cough - mild or absent on a patient reported scale of severe, moderate, mild, absent
- Frequency of CNS symptoms (e.g. headache, dizziness, impaired consciousness, ataxia, acute cerebrovascular disease, and epilepsy)
- Frequency of respiratory progression:

Defined as  $\text{SpO}_2 < 94\%$  on room air or  $\text{PaO}_2/\text{FiO}_2 < 300$  mmHg and requirement for supplemental oxygen or more advanced ventilator support

- Proportion of Participants Discharged by Day 14
- The mortality rate of subjects at week 2 and week 3

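### Section 3.5.1 lists severe events, including progression to severe pneumonia, as off-study criteria without separating stopping treatment from leaving follow-up, so late endpoint data may be lost in the sickest subjects

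*Protocol*

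**What the plan says.** The heading of protocol Section 3.5 names two things: "CRITERIA FOR REMOVAL FROM PROTOCOL THERAPY AND OFF STUDY CRITERIA". Only one subsection follows, 3.5.1, and it is titled as the off-study list. It consists of a sentence fragment covering participants with liver toxicity of grade 3 or 4, allergic reaction of grade 3, "or other severe adverse events (including progression to the stage of severe pneumonia"). The fragment has no main verb. It does not say what happens to these participants, and no list is given for stopping treatment alone.

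The endpoints need observation at fixed later times:

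- Section 6.2.1 (primary): the change from positive to "negative results in respiratory tract specimen on day 0, 2, 4, 6, 8, 10, 12, 14".
- Section 6.3.1 (secondary): virological clearance at Day 8, "AUC of viral load on day 0, 2, 4, 6, 8, 10, 12, 14", and time to clinical recovery, which must be sustained for 72 hours.
- The remaining secondary endpoints include "Proportion of Participants Discharged by Day 14" and mortality at weeks 2 and 3.

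Section 2.1.1 limits entry to mild or moderate disease and defines the upper end as "Adult with pneumonia but no signs of severe pneumonia and no need for supplemental oxygen". Section 3.1 separately lets investigators move a subject to the HCQ arm on Day 8 for progression of pneumonia.

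**The concern.** No subject can have severe pneumonia at entry. Reaching it after randomisation is therefore an outcome, and it marks the subjects with the worst prognosis. A rule that labels them off-study can be read at a site as an instruction to stop swabs, clinical assessments and vital-status checks. The loss would then depend on outcome and, in an open-label trial, could differ between arms in either direction.

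This is a matter for the protocol and not for the SAP. An SAP can decide how to handle missing values, but it cannot restore a swab that was not taken or a vital status that nobody sought. The endpoints most exposed are mortality and viral-load AUC.

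**Working it through.** **Step 1: what each endpoint needs after a 3.5.1 event.** This assumes that off-study is taken to end data collection.

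| Endpoint | Needs data until | Lost after the event? |
|---|---|---|
| Time to negative rRT-PCR (6.2.1) | Day 14 | Yes, if still positive at the last sample |
| Virological clearance (6.3.1) | Day 8 | Only if removed before the Day 8 sample |
| Viral-load AUC (6.3.1) | Day 14 | Yes |
| Time to clinical recovery (6.3.1) | Recovery sustained for 72 hours | Yes, if not yet recovered |
| Respiratory progression (6.3.1) | The event itself | Largely no: met at or before removal |
| Discharge (6.3.1) | Day 14 | Yes |
| Mortality (6.3.1) | Weeks 2 and 3 | Systematic follow-up lost; some deaths may be reported as serious adverse events |

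**Step 2: viral-load window.** Inputs: the eight sampling days 0, 2, 4, 6, 8, 10, 12 and 14 (Section 6.3.1). If the last sample is on day d, the samples lost are (14 − d)/2 and the share of the window lost is (14 − d)/14.

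| Last sample | Samples lost (of 8) | Window lost |
|---|---|---|
| Day 2 | 6 | 12/14 = 86% |
| Day 4 | 5 | 10/14 = 71% |
| Day 6 | 4 | 8/14 = 57% |
| Day 8 | 3 | 6/14 = 43% |

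These figures are calendar arithmetic for one affected subject. They do not say how many subjects are affected.

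**Step 3: mortality.** Inputs: the planned 30 HCQ and 15 SOC subjects (Section 3.1; 30/15 = 2, which agrees with the 2:1 ratio). One subject with unknown vital status may be alive or dead, so the range from best to worst case widens by

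- HCQ: 1/30 = 3.3 points;
- SOC: 1/15 = 6.7 points;
- one in each arm, for the difference between arms: 3.3 + 6.7 = 10.0 points.

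**Step 4: several removals.** The protocol gives no removal rate, so the counts below are assumptions. Assume also no deaths among subjects who stay, and unknown vital status for all who are removed. The HCQ minus SOC difference then runs from −(SOC removed)/15 to +(HCQ removed)/30.

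| Removed, HCQ and SOC | Range of the difference (points) |
|---|---|
| 2 of 30 and 1 of 15 | −6.7 to +6.7 |
| 3 of 30 and 2 of 15 | −13.3 to +10.0 |
| 6 of 30 and 3 of 15 | −20 to +20 |

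With 45 subjects, a handful of removals would leave the mortality comparison undetermined.

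**The case against.** The strongest reply is that 3.5.1 never says observation ends. Its parent heading also speaks of removal from therapy, and the endpoint sections make no exception for subjects who meet 3.5.1. A mortality endpoint would also make little sense if follow-up ended at severe pneumonia. If 3.5.1 is read as a list for stopping treatment, the sections agree with each other. That is a fair reading, and it may be what was meant. It is not what the label says, and no text shown tells a site to prefer it. What stands from this objection is that the loss is conditional on how sites read the label.

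Three further points:

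- **Sections 3.2 to 3.4 are not shown.** A follow-up rule there could define the label and settle the matter, so its absence cannot be claimed. If one exists, 3.5.1 should point to it.
- **Deaths may still be captured.** Section 7.1.4 counts death as serious and Section 7.2 has serious events reported, with no stated cut-off at off-study. This stands in part: event reporting may catch deaths, but it is not scheduled confirmation that the others are alive at weeks 2 and 3.
- **The Day 8 switch in Section 3.1 is not a contradiction.** It is permissive and covers any progression of pneumonia, while 3.5.1 concerns severe pneumonia. They overlap at the severe end, and which applies there is not stated.

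A reader might infer support for the literal reading from two other places. Section 2.3 says "Replacement subjects will be assigned the corresponding number, starting from 101", and Section 3.1 says that "the safety and tolerability of HCQ will be evaluated during treatment period in COVID-19 patients". Neither carries that weight. The first does not say which subjects are replaced and does not refer to 3.5.1. The second concerns safety and tolerability, not efficacy sampling or vital status.

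**Conclusion.** The point holds as an ambiguity with a conditional consequence, and it should be fixed. Section 3.5 announces two concepts and delivers one list, under the label that implies the greater loss. Applied literally, that label is at odds with the endpoints in Sections 6.2.1 and 6.3.1.

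The size rests on one assumption, that off-study ends collection. Given that, an affected subject loses 43% to 86% of the AUC window if removed after the Day 8 to Day 2 sample, and each unknown vital status adds 3.3 (HCQ) or 6.7 (SOC) points to the mortality range. The number of subjects affected is unknown. Deaths caught by serious adverse event reporting would narrow the mortality range.

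Two stronger readings are not supported. One is that the protocol orders data collection to stop; the fragment does not say so. The other is that the primary comparison is biased by some stated amount. That would depend on how removed subjects are analysed and on how losses fall between arms, and this protocol settles neither. Confidence is moderate because of the unseen sections and the conditional harm.

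**What to change.** In Section 3.5.1, separate discontinuation of study treatment from leaving the study. State that every randomised subject, unless consent is withdrawn, continues the already scheduled rRT-PCR sampling to Day 14, the clinical and discharge assessments, and vital status to week 3. If an unseen section already provides for this, refer to it and bring the label into line.

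Reconcile 3.5.1 with the Day 8 switch text in Section 3.1, so that it is clear how the two relate when pneumonia becomes severe. No stopping or switching rule is proposed here.

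The cost is a few sentences of protocol text, plus a small burden of continued swabs and assessments in the few subjects affected, some of whom may have moved to a higher level of care.
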